1.0 PROTOCOL SUMMARY AND/OR SCHEMA

This trial will investigate the feasibility of implanted anchored Beacon® electromagnetic lung transponders (Calypso®) to guide and monitor deep-inspiration breathhold (0IBH) treatments in patients with inoperable thoracic malignancies. Currently, many patients with thoracic tumors cannot be treated to the optimal intended radiation dose due to strict dosimetric limitations for normal tissues nearby. Furthermore, all lung tumors that are treated to the full radiation dose exhibit tumor motion with respiration which requires the radiation field to be expanded to an internal target volume (ITV) that encompasses all possible tumor positions during the treatment in order to avoid missing the target. This results in the unnecessary treatment of larger amounts of normal lungs, esophagus and other nearby organs at risk which are responsible for the majority of adverse events in thoracic radiation oncology.

Several techniques to reduce respiratory motion during radiation therapy have been explored and are clinically available. One of the most promising approaches is to immobilize the tumor by having patients hold their breath. This has been found to result in effective reduction of tumor motion as well as an expansion of the lungs and other normal tissues to be moved away from the radiation target. However, 0IBH is currently performed based on external markers and radiographic surrogates such as the diaphragm to monitor the patient's breathhold. It is known that external markers and the diaphragm frequently do not correlate well with internal motion and tumor position. Using implanted Calypso beacons would for the first time allow real-time monitoring of tumor position and breathhold in patients with thoracic malignancies. This technology was initially developed for prostate cancer patients with great success. A new anchored lung transponder has been developed for its application in thoracic malignancies in which there is significantly more tumor motion. Based on our experience in prostate cancer patients, it is our expectation that this transponder would improve the reproducibility of localizing and monitoring tumor position during breathhold in real time, decrease radiation dose to organs at risk in close proximity to the radiation target and allow dose escalation to desired radiation doses. In addition, limiting tumor motion to a minimum and thus increasing our confidence in intrafraction tumor position would allow decreasing the ITV margins that are currently added to the tumor to account for tumor motion. This would ultimately lead to improved local control rates and decreased adverse events attributable to the radiation treatments.

[figure not shown]
Patients who are able to hold their breath at least for 5 breathholds of more than 20 seconds each and are planned to undergo radiation treatment to tumors in the thorax will be eligible for this study.

First, 2-3 anchored lung transponders will be placed bronchoscopically in or near the target tumor. Patients will be given instructions to learn and practice the 0IBH maneuver. After a minimum of 3 days, the patient will undergo a CT simulation for radiation treatment planning, and a free-breathing 40 CT scan and a CT scan in 0IBH will be obtained using the Varian® Real-time Position Management™ (RPM) system. Two radiation therapy plans will be developed, one based on the free-breathing 40 CT scan and one based on the 0IBH scan. At the time of treatment, the patient will be initially positioned according to standard setup

procedures based on external tattoos and room lasers. A free- breathing trace of the Calypso transponders will be obtained to allow the patient to settle on the treatment table and to study real-time respiratory traces. The patient will then be asked to perform a therapist-coached modified slow vital capacity maneuver and DIBH maneuver [1] and hold their breath. Patients will have the ability to perform this maneuver with or without biofeedback from digital goggles that are placed over the patient's eyes and display the breathing trace of the Calypso transponders. The use of the digital goggles will be determined by patient preference or at the discretion of the treatment team. This will allow us to investigate whether real-time biofeedback adds to the reproducibility of patients holding their breath. A DIBH cone-beam CT will be acquired in approximately three breath-holds, once a week for standard fractionated RT patients or with each fraction for SBRT patients. After review and approval of the images, the patient will be treated while holding their breath using the DIBH maneuver. In standard fractionated RT patients the radiation treatment will be guided by the external tattoos and daily 2D kV imaging. The Calypso transponder signal will be used to monitor the level of the breath-hold during treatment. The breath-hold level based on the Calypso transponder signal will be verified daily by the 2D imaging and once a week in 3D by the DIBH cone-beam CT. In SBRT patients, the radiation treatment will be guided by the external tattoos and daily DIBH cone-beam CT. The Calypso transponder signal will be used to monitor the level of the breath-hold during treatment. The therapists will monitor the respiratory trace signal from the Calypso transponders throughout the treatment and will initiate the radiation treatment delivery when the patient holds his/her breath within the tolerance level the patient has been assigned to. This will be continued up until the initially planned 30 patients are accrued.. Should the transponder signal indicate that the target has moved outside of the preset tolerance, the therapists will hold further radiation treatment delivery until the patient's breathhold has returned to the desired target range or until the patient's setup has been corrected. In the additional 25 patients planned, the margins will be reduced in a step-wise fashion. The gate will be decreased 1mm per each set of 5 patients until the duty cycle (beam-on time) and number of DIBH attempts are doubled. The gate at which this occurs will be considered the minimum clinically feasible gate

The study will determine for the first time based on real-time tumor positioning information whether patients are able to reproducibly hold their breath in DIBH within excursions of 5.+-0.5cm or less. Furthermore, it will determine whether visual biofeedback improves the reproducibility of the breathhold. It will provide a unique dataset that will allow us to determine the concordance level of real-time tumor position information from the Calypso transponders, external surface signal and radiographic imaging. Ultimately, this study will allow us to quantify the decrease in radiation dose to organs at risk, decreased toxicity and amount of dose escalation made possible by the DIBH maneuver using real-time tumor position information.

Patients will be considered evaluable for protocol when they have had successful calypso beacon implantation without the beacons migrating> 5cm, and they have completed training in DIBH. In the extension of the protocol described below, 25 patients will be accrued; the expected time for completion of this study is 3 year from its approval.

2.0 OBJECTIVES AND SCIENTIFIC AIMS

Primary objectives:

- To evaluate the feasibility of using internal tumor surrogates (Calypso beacons) during repeated deep inspiration breath hold maneuvers for DIBH radiation treatments.

Secondary objectives:

- To compare the reproducibility with visual versus without visual biofeedback.
- To assess differences in the ability of maintaining the DIBH maneuver within the gate with and without visual biofeedback
- To measure the residual intrafraction tumor motion and associated improvement in normal tissue dosimetry during DIBH based on the Calypso lung transponder signal as a surrogate
- To measure the increase in dose escalation and the potential for decreasing margins made possible by Calypso-guided DIBH
- To determine the minimum clinically feasible gate margin for radiation
- To assess tumor shrinkage, beacon position and centroid changes in conventionally fractionated patients
- To assess intra- and inter-fraction variation in lung volume preservation of multiple DIBH maneuvers

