3.0 BACKGROUND AND RATIONALE

3.1 Respiratory motion in lung cancer radiation treatment

Non-small cell lung cancer (NSCLC) remains the malignancy associated with the highest number of cancer-related deaths in the US.

Patients with inoperable early-stage NSCLC are typically treated with high-dose stereotactic body radiation therapy (SBRT) resulting in excellent local control of >90%. [2-5] SBRT is now also being used for metastatic disease in the lungs, with equally good local control rates and low rates of toxicity as observed in early-stage NSCLC. [8-11] Currently, a 4D free breathing CT scan is obtained at simulation. The 4D scan is used to determine the entire volume swept out as the tumor moves through the respiratory cycle. This volume (the ITV) is further increased by the addition of 0.5 to 1 cm margins of healthy tissue to create the volume (the target) which is treated to the prescription dose. The margins of healthy lung are needed to account for positioning uncertainties during treatment. Significant respiratory tumor motion results in an increase of the ITV and therefore the volume of healthy lung within the target volume. The volume of healthy lung within the target, and the volumes of adjacent normal tissues such as chest wall increase rapidly with increasing ITV size. Since these patients are usually medically inoperable due to severe emphysema or other medical comorbidities, any reduction in radiation dose to organs at risk is desirable. The most common toxicities observed with SBRT include respiratory toxicity, esophagitis, chest wall pain, and rib fractures. The rate of toxicities from SBRT appears to be directly related to the irradiated volume, the tumor

location and the radiation dose.[5-7]

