Locally-advanced NSCLC patients receive fractionated RT, ideally 60 Gy in 30 fractions when given with concurrent chemotherapy.[12-14] Frequently, the predicted toxicity from radiation dose to the lungs and spinal cord using widely agreed upon dose constraints to these organs limit our ability to treat patients to the optimal prescription dose. [15, 16] Respiratory motion can significantly increase the treated volume, especially in patients with already large tumors. The most common toxicities in this patient population are esophagitis and respiratory toxicity including radiation pneumonitis.[14, 17] The same challenges exist for patients with limited-stage small cell lung cancer treated with chemotherapy and thoracic radiation therapy.[18-20] Techniques to address intrafraction tumor motion include abdominal compression, respiratory gating, and active breathing control (ABC).[21] While these are all clinically approved techniques, they are not currently widely used in practice. Abdominal compression can be uncomfortable to the patients and does not necessarily control internal motion well.[22] In addition, it compresses the lungs and does not consistently improve sparing of normal tissues, but may actually worsen the dosimetry.[23] Respiratory gating based on external markers can be misleading due to the potential discrepancy between external marker and true internal target motion.[24, 25] ABC is an involved process using a spirometer which is frequently uncomfortable to the patient, and there are problems with changes in tidal volume, volume expansion, patients' response and adaptation to the system.[26, 27] These techniques all depend on unreliable surrogates of the target position, and frequently cannot be tolerated by patients because of patient discomfort or are too complex for patients to manage, making them far from ideal .

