6.0 CRITERIA FOR SUBJECT ELIGIBILITY

6.1 Subject Inclusion Criteria

- Patients must have histologic proof of malignancy suitable for thoracic radiation therapy
- Patients planning to undergo radiation therapy for primary or recurrent malignancy of the lung or metastatic malignancy to the lung.
Note: this may be delivered by SBRT or standard fractionation, based on the discretion of the treating physician.
- Age 18 years old
- KPS 60%
- Ability to hold their breath for >20 seconds for 5 times
- Patients who are able to tolerate flexible bronchoscopy
- Patients with life expectancy of at least 12 months
- Patients able to have bronchoscopic placement of Calypso transponders as confirmed on a recent (within the past 8 weeks) CT scan.
- Patients who are able to comply with the protocol follow-up schedule.

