In the additional 25 patients to be accrued the window will be reduced in a step-wise fashion by 1mm for every 5 patients. Number of beam holds, treatment interruptions and total treatment time from first beam-on time to the last beam-off time will be recorded by the therapists.

If a patient cannot achieve the desired breath hold after 3 attempts and discussion with the therapist, the therapist can treat with the best breath-hold achievable and report the change in level to the treating physician. Additionally, the therapist will acquire an orthogonal pair of images. The physicist will then estimate the dosimetric effects per day in case the patient is still unable to achieve adequate breath hold the next day. Depending on the estimated dosimetry and the patient's reasons for not being able to achieve breath hold, the patient may be taken off protocol if unable to perform the breath hold to within +/- 5 mm for 3 consecutive treatment days. Patients who are taken off protocol prior to treatment completion will be treated based on the free-breathing treatment planning scan for the remainder of the radiation treatment course.

9.1 For patients undergoing SBRT in 10 or less fractions, the following procedures will be performed:

1. Standard setup procedures based on external tattoos will be performed.
2. The Calypso antenna will be deployed and positioned over the patient's chest. Tracking of the Calypso transponder signal will commence.

3. For patients who have been selected to use the digital goggles, the DIBH maneuver will be performed with visual biofeedback at least once a week and at least one fraction will be done without visual feedback. During treatment the radiation therapist will coach the patient on how to hold their breath during the treatment. On treatment days with visual feedback, the patient will be able to view and control his/her breathing through biofeedback using goggles (Myvu Personal Media Viewer, Myvu Corporation) or an iPhone that displays the Calypso trace. The couch position will be adjusted by the therapists in the treatment room to accurately set up the patient for treatment in DIBH based on the Calypso signal. The Calypso trace will be set to zero based on the DIBH level.
4. The patient will resume regular breathing and the therapists will leave the room.

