For the 1st secondary objective, we will compare the visual vs no visual biofeedback treatments (for patients who agree to use the digital goggles) by the number of treatment interruptions. We expect that there will be fewer treatment interruptions when using biofeedback. To this end Wilcoxon signed-rank tests will be conducted based on the patients who can successfully be treated.

For the 2nd secondary objective, we will assess differences in the ability of maintaining the DIBH maneuver within the fate with and without visual biofeedback. Such differences will be measured as duty cycle, and will be compared using Wilcoxon signed-rank tests based on the patients who can successfully be treated.

For the 3rd secondary objective, the residual intrafraction tumor motion (surrogated by Calypso) will be measured in all 3 dimensions and the euclidean distance will be calculated, which will then be correlated with the normal tissue dosimetry (see end of Section 12.0). Patients will receive multiple fractions and thus multiple measurements of such distance will be obtained from the same patients.

These repeated measures will be averaged for each patient and the correlation will be examined by simple linear regression. If such continuous data are skewed, we may either use an appropriate monotone transformation, or examine the nonparametric correlation coefficient (such as Spearman rank correlation coefficient) between the tumor motion and the normal tissue dosimetry instead.

For the 4th secondary objective, the potential increase in dose escalation and decrease in margins made possible by Calypso- guided DIBH, as contrasted to those obtained from the 40 CT scan, will be formulated as pair data from each patient and tested by using Wilcoxon signed-rank tests. Dosimetric parameters listed at the end of Section 12.0 will be used again for such analysis.

The 5th secondary objective does not require statistical analysis. See Section 12.0 for details.

For the 6th secondary objective, tumor shrinkage, beacon position and centroid changes in conventionally fractionated patients (totally 10), all measured as continuous variables, will be summarized descriptively.

For the 7th secondary objective, intra- and inter-fraction variation in lung volume preservation of multiple DIBH maneuvers will be recorded within each patient and summarized descriptively.

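### The regression of normal tissue dosimetry on residual motion (3rd secondary objective) pools SBRT and conventional patients with no schedule term, so its slope is confounded if motion also differs by schedule

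*Combined protocol and SAP*

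**What the plan says.** Both schedules enter one study. The note in Section 6.1 says of the radiation therapy that "this may be delivered by SBRT or standard fractionation, based on the discretion of the treating physician".

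The background describes different patients under each schedule. Section 3.1 links SBRT to inoperable early-stage disease and to lung metastases, and Section 9.1 sets its fraction number: "For patients undergoing SBRT in 10 or less fractions, the following procedures will be performed". On the other schedule, Section 3.1 says: "Locally-advanced NSCLC patients receive fractionated RT, ideally 60 Gy in 30 fractions when given with concurrent chemotherapy". In that paragraph it adds: "Respiratory motion can significantly increase the treated volume, especially in patients with already large tumors".

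Section 2.0 gives the 3rd secondary objective as "To measure the residual intrafraction tumor motion and associated improvement in normal tissue dosimetry during DIBH". For this objective, Section 14.0 reduces the three-dimensional motion to a Euclidean distance, obtained repeatedly over fractions. It then says: "These repeated measures will be averaged for each patient and the correlation will be examined by simple linear regression". A transformation or a Spearman coefficient is allowed if the data are skewed. The outcome is the set of dosimetric parameters at the end of Section 12.0, among them lung V20, mean lung dose, chest wall V30, and esophageal and cord dose. For the 4th objective, free-breathing and DIBH plan values are paired within patient and compared by Wilcoxon signed-rank tests.

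Neither analysis names schedule as a covariate, stratum or subgroup. The plan does split patients elsewhere: the primary objective by enrolment set, and the descriptive 6th objective by restriction to conventional patients. Pooling is therefore the natural reading for the 3rd objective.

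**The concern.** Early-stage or metastatic lesions treated in 10 or fewer fractions and locally advanced tumors treated in about 30 are likely to give different values of lung V20, mean lung dose, and esophageal and cord dose. If mean residual motion also differs between the two groups, schedule is linked to both variables in the regression. The slope then mixes any real relation between motion and dosimetry with the contrast between two patient groups. A reader would take a significant slope as evidence that steadier breath-holds give better dosimetry, when it could arise with no such relation inside either schedule.

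The documents do not report residual motion by schedule, but they leave room for a difference:

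- The per-patient averages cover 10 or fewer fractions under SBRT and about 30 under conventional treatment.
- SBRT has cone-beam CT at each fraction. Conventional patients have daily kV images and weekly cone-beam CT.
- At least 10 additional conventional patients are planned alongside the extension in which the tolerance window narrows in 1 mm steps (Sections 4.1 and 12.0), so schedule may partly track permitted motion.

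**Working it through.** The plan gives no sample size, power or alpha for this objective, so there is no figure of its own to reproduce. The check asks how often the pooled regression is significant when nothing relates motion to dosimetry inside either schedule.

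**Inputs from the documents.** There are two sets of 25 evaluable patients (Section 14.0), hence N = 50 pooled or N = 25 for one set. At least 10 additional conventional patients are planned (Section 4.1). The schedule mix of the first set is not stated.

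**Assumed inputs.** Two-sided 5% test; share conventional p = 0.40 (0.20 as a variant); within-schedule motion SD 0.8 mm; difference in mean motion between schedules d = 0 to 0.8 mm. Section 14.0 does not say whether the outcome is the absolute dose parameter or the DIBH improvement, so both are taken:

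- absolute lung V20: 5% (SD 2.5) SBRT, 22% (SD 6) conventional;
- DIBH gain in percentage points: 1.5 (SD 1) SBRT, 4 (SD 3) conventional.

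**Spurious correlation.** With no within-schedule relation, w = p(1 − p), motion difference d and dosimetry difference D, the pooled correlation is

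r = w·d·D / √[(s_M² + w·d²)(s_D² + w·D²)],

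where s_M² and s_D² are the average within-schedule variances. Take w = 0.4 × 0.6 = 0.24 and d = 0.5. The motion term is 0.64 + 0.24 × 0.25 = 0.70.

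- V20: D = 17; s_D² = 0.4 × 36 + 0.6 × 6.25 = 18.15; r = 2.04 / √(0.70 × 87.51) = 0.26.
- Gain: D = 2.5; s_D² = 0.4 × 9 + 0.6 × 1 = 4.2; r = 0.30 / √(0.70 × 5.70) = 0.15.

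If d = 0 the numerator is zero, however large D is.

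**Simulated false-positive rate of the pooled slope** (V20 rows 4,000 runs per setting; Monte Carlo standard error at 46% is √(0.46 × 0.54 / 4000), or 0.8 percentage points):

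| Setting | d = 0 | 0.25 mm | 0.5 mm | 0.8 mm |
|---|---|---|---|---|
| V20, N = 50, 40% conventional | 5% | 16% | 46% | 84% |
| V20, N = 50, 20% conventional | 6% | 12% | 34% | 68% |
| V20, N = 25, 40% conventional | 5% | 10% | 26% | 54% |
| Gain, N = 50, 40% conventional | 5% | 9% | 18% | 36% |

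For the gain at N = 25 and 0.5 mm the rate is about 12%. Pooled Spearman for V20 at N = 50 and 0.5 mm gives about 40%, so the nonparametric fallback does not help. With schedule in the model the rate is about 5% throughout.

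**Standardised version.** In within-group SD units, with 20 of 50 patients in one schedule, differences of 0.5 SD in motion and 1 SD in dosimetry give 11.2%. Differences of 1 and 2 SD give 61.4%. With a schedule term every scenario lies between 4.4% and 5.7%.

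**Paired tests (4th objective).** With no effect in either schedule, the pooled signed-rank test rejects in 4.0% to 5.2% of runs, even when one group's spread is five times the other's. With an effect of 3 within-group SDs in 10 of 25 patients and none in the other 15, it rejects in about 92%. That is a true overall rejection which does not describe both groups.

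**The case against.** The strongest reply is that the confounding needs a premise the documents do not supply. A reader might infer that schedule alone can produce a correlation, because doses and tumors differ. It cannot: with equal mean motion the error stays at 5% however far dosimetry differs. No section reports residual DIBH motion by schedule, and both schedules are treated within an assigned tolerance window with automatic beam hold, which limits how far the groups can diverge. This stands, and it makes the concern conditional.

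The size is also uncertain. Section 2.0 speaks of an improvement in dosimetry, and Section 12.0 derives improvement from the free-breathing and DIBH plans of the same patient. If the gain is the outcome, the rate at 0.5 mm is about 18%, not 46%. If relative gains are similar in the two schedules (30% versus 25%, SD 15, also assumed), it is 5% to 6%.

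A reader might further infer that the paired tests are faulty because one schedule can drive them. The documents do not support that. Schedule is constant within a patient, so it cannot confound a within-patient comparison, and the type I error holds. Nothing in the documents suggests that DIBH worsens SBRT plans.

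Nor do the documents show that the schedules differ by design in dose or target size. Schedule is at the physician's discretion, SBRT is the one called high-dose, no SBRT dose in Gy is given, and no target volumes are given for either group. Respiratory toxicity and esophagitis are listed for both. The expected difference in dosimetry is an inference from disease stage and fractionation.

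Finally, the objective is secondary and exploratory, with no decision rule. That limits the stakes but does not answer the point, since the remedy costs almost nothing.

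**Conclusion.** The concern holds in conditional form. Section 14.0 regresses dosimetry on mean residual motion across two schedules with different disease and fractionation, and has no term for schedule. If both motion and dosimetry differ by schedule, the slope is confounded. At N = 50 with 40% conventional and a 0.5 mm motion difference, the false-positive rate is about 46% or about 18%, depending on which outcome is meant, against 5% after adjustment. The motion difference, SDs, dosimetry means and schedule mix are all assumptions. The documents settle none of them, and with no motion difference there is no inflation.

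The point concerns the 3rd secondary objective only. The pooled paired tests of the 4th objective are valid as overall tests, and the primary feasibility analysis is untouched.

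**What to change.** In Section 14.0, add treatment schedule (SBRT versus conventional) as a covariate in the 3rd-objective regression. If the Spearman route is taken, use a partial Spearman coefficient adjusted for schedule. It would help to state in the same place whether the outcome is the absolute parameter or the free-breathing-to-DIBH difference, since the size of the problem depends on it.

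Optionally, for the 4th objective, report the median paired difference with a confidence interval by schedule, labelled as description alongside the overall test.

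The cost is one degree of freedom and a few lines of text. Each patient's schedule is known, so no new data are needed and no treatment rule changes.
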